#### Table 15.3.3.2 Incidence of Arterial Blood Gas Analysis Abnormalities – Safety Set

Number and percentage of patients with abnormal values will be displayed by HTD and overall in Not CS abnormal and CS abnormal categories. Percentage will be based on the number of patients at specified visit.

#### Table 15.3.3.3 Shift Table of Arterial Blood Gas Analysis Results – Safety Set

Shift tables showing changes in the number and frequency of patients in Not CS abnormal and CS abnormal categories between baseline and MPV3/EDV will be provided.

#### Table 15.3.3.4.1 Summary of Peripheral Oxygen Saturation (%) by HTD – Safety Set

#### Table 15.3.3.4.2 Summary of Peripheral Oxygen Saturation (%) – Safety Set

The default summary statistics of peripheral oxygen saturation (%) will be presented by HTD and overall at visits A1 and MPV3. The absolute change from baseline will be presented as well. For the changes from baseline a 95% confidence interval will be provided.

#### Listing 16.2.4.3 Arterial blood gas analysis – Enrolled Set

Values of arterial blood gas analysis and peripheral oxygen saturation (%) will be listed.

### **5.6.4 Vital Signs**

Vital signs will be collected at screening (V1), visits A1, A3/B3/C3/D3, MPV1, MPV2, MPV3/EDV and FUV2. Blood pressure and heart rate will be measured in supine position (two measurements) and afterwards in standing position (one measurement). Tympanic body temperature will also be assessed.

At visits A1 and MPV3, blood pressure and heart rate will be measured before IMP intake as well as 4, 8 and 24 hours after IMP intake. For patients enrolled under protocol version final 1.0, vital signs were only evaluated before IMP intake.

Systolic and diastolic blood pressure and pulse rate will be summarised by measurement position. The mean value of measurements in the supine position at a given timepoint will be used in summaries. **Orthostatic changes** in vital sign parameters will also be calculated as the difference between the measurement in the standing position and the mean of the supine measurements. The orthostatic changes will be displayed after each corresponding parameter's standing position results in summaries.

To evaluate the short-term effects of the IMP on vital sign parameters, the absolute change from the pre-dose value within the corresponding visit will be calculated for each parameter at visits A1 and MPV3. Additionally, the difference in the within-visit changes will be evaluated for each corresponding timepoint between visits MPV3 and A1.

**Physical measurements** – height and weight will be assessed at visit V1. Weight will also be measured at MPV3/EDV. BMI will be calculated from available data (see Section 5.2.1 for calculation).

The following statistical output will be provided:

Table 15.3.4.1.1 Summary of Vital Signs by HTD– Safety Set

Table 15.3.4.1.2 Summary of Vital Signs – Safety Set

Vital sign parameters will be summarised including change from baseline at each timepoint by HTD and overall.

Table 15.3.4.2 Summary of Vital Signs by Pooled HTD – Safety Set

Vital sign parameters will be summarised as above, with HTD pooled into “HTD < 200 mg” and “HTD 200 mg” groups.

Table 15.3.4.3.1 Summary of Short-Term IMP Effect on Vital Signs by HTD – Safety Set

Table 15.3.4.3.2 Summary of Short-Term IMP Effect on Vital Signs – Safety Set

The observed values and absolute changes from the pre-dose value will be summarised for each vital sign parameter at each timepoint by HTD and overall.

Table 15.3.4.4.1 Summary of Change in Short-Term IMP Effect on Vital Signs by HTD – Safety Set

Table 15.3.4.4.2 Summary of Change in Short-Term IMP Effect on Vital Signs – Safety Set

The changes from pre-dose values and the differences in changes from pre-dose values will be summarised between corresponding timepoints at visits A1 and MPV3 by HTD and overall.

Table 15.3.4.5.1 Summary of Physical Measurements by HTD – Safety Set

Table 15.3.4.5.2 Summary of Physical Measurements – Safety Set

Physical measurements will be summarised including change from baseline at each timepoint by HTD and overall.

Figure 15.3.1 Vital Signs Median Change from Baseline – Safety Set

The median changes from baseline of vital signs parameters at each post-baseline timepoint will be displayed by will be displayed by HTD. The HTD will be pooled into “HTD < 200 mg” and “HTD 200 mg” groups.

Listing 16.2.4.4 Vital Signs and Physical Measurements – Enrolled Set

Values of vital signs and physical measurements will be listed.

## 5.6.5 12-Lead Electrocardiogram (ECG) Data

A simultaneous 12-lead resting electrocardiogram (ECG) will be collected at screening (V1), A1, A3/B3/C3/D3, MPV1, MPV2, MPV3/EDV and FUV2. At visits A1 and MPV3 triplicate ECG recordings will be performed at following time points - before IMP intake as well as 4 and 8 hours after IMP intake. At EDV only one ECG recording will be performed. For patients enrolled under protocol version final 1.0, ECG assessments were only collected once at visits V1, A3/B3/C3/D3, MPV1, MPV3/EDV.

Following parameters will be assessed:

- Heart rate (bpm)
- P-R interval (msec)
- QRS duration (msec)
- QTcF interval (msec)
- QT interval (msec)
- P pulmonale
- Right axis deviation
- RV hypertrophy
- RV strain
- Right bundle branch block
- Heart rhythm (normal, abnormal)

For patients enrolled under protocol version final 1.0, heart rhythm was not collected.

Clinical significance (yes/no) of any abnormal ECG data findings will be assessed by the investigator. Parameter values without a clinical significance evaluation will be considered as “Normal”, and values with “No” or “Yes” clinical significance evaluations will be considered as “NCS Abnormal” and “CS Abnormal”, respectively.

Where multiple ECG recordings are performed within a visit or timepoint, ECG parameters will be summarised as follows. For numeric parameters, the mean of collected values will be used in summaries. For abnormality assessments, the worst value within the visit/timepoint will be used.

To evaluate the short-term effects of the IMP on ECG parameters, the absolute change from the pre-dose value within the corresponding visit will be calculated for each parameter at visits A1 and MPV3. Additionally, the difference in the within-visit changes will be evaluated for each corresponding timepoint between visits MPV3 and A1.

The following statistical output will be provided:

Table 15.3.5.1.1 Summary of ECG Assessments by HTD – Safety Set

Table 15.3.5.1.2 Summary of ECG Assessments – Safety Set

ECG parameters will be summarised including change from baseline at each visit by HTD and overall.

Table 15.3.5.2.1 Summary of Short-Term IMP Effect on ECG Assessments by HTD – Safety Set

Table 15.3.5.2.2 Summary of Short-Term IMP Effect on ECG Assessments – Safety Set

The observed values and absolute changes from the pre-dose value will be summarised for each vital sign parameter at each timepoint by HTD and overall.

Table 15.3.5.3.1 Summary of Change in Short-Term IMP Effect on ECG Assessments by HTD – Safety Set

Table 15.3.5.3.2 Summary of Change in Short-Term IMP Effect on ECG Assessments – Safety Set

The changes from pre-dose values and the differences in changes from pre-dose values will be summarised between corresponding timepoints at visits A1 and MPV3 by HTD and overall.

Table 15.3.5.4.1 Incidence of ECG Abnormalities – Safety Set

Number and percentage of patients with Not CS abnormal and CS abnormal ECG parameters assessments will be displayed by HTD and overall. Percentage will be based on the number of patients at specified visit.

Table 15.3.5.4.2 Shift Table of ECG Abnormalities – Safety Set

Shift tables showing changes in the number and frequency of patients in not CS abnormal and CS abnormal categories between baseline and MPV3/EDV will be provided. The worst abnormality assessment collected during MPV3/EDV will be selected for each patient. Percentage will be based on the number of patients in the safety set.

Table 15.3.5.4.3 Shift Table of Within-Visit ECG Abnormalities – Safety Set

Shift tables showing changes in the number and frequency of patients in not CS abnormal and CS abnormal categories between the pre-dose measurement and each post-dose measurement at each visit.

The worst abnormality assessment collected during the corresponding timepoint will be selected for each patient. Percentage will be based on the number of patients in the safety set.

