### 4.1 General Methodology and Presentation of the Results

The default summary statistics for quantitative (continuous) variables will be

- the number of patients (n),
- mean,
- standard deviation (SD),
- coefficient of variation (%CV),
- median,
- minimum (min) and maximum (max)

for patients with data.

Mean and median will be presented to one more decimal place than the raw value. The minimum and maximum values will be presented with the same decimal precision as the raw value. SD will be reported to two decimal places greater than the original value, however no more than 3 decimal places will be presented. CV will be reported to one decimal place.

For qualitative (categorical) variables, the frequency count (n) and percentage (%) of patients with non-missing data per category will be the default frequency tabulations. Where appropriate and present, the number of missing values will be displayed as “Missing” category.

Percentage values are to be presented to one decimal place, for example, 52.3%.

The denominator used for calculation of the percentages will be specified in a footnote to the tables for clarification.

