### 5.6.1 Adverse Events

AEs will be coded according to latest Medical Dictionary for Regulatory Activities (MedDRA®) Version 22.0.

Adverse events' data include:

- adverse event name
- start/stop dates
- ongoing
- severity (mild, moderate, severe)
- relationship (not related, unlikely, possible, probable, definite)
- action taken with study medication (dose not changed, dose reduced, drug interrupted, drug withdrawn, not applicable, unknown)
- other actions (none, medication required, tests required, withdrawn from the study, hospitalisation required or prolonged, other specification)

- outcome of event (recovered/resolved, recovering/resolving, not recovered/not resolved, recovered/resolved with sequelae, fatal, unknown)
- AE of special interest (yes or no)
- seriousness (yes or no)
- start/stop dates of drug interruption

All AEs will be presented in listings.

Summaries of adverse events will include AEs defined as **treatment-emergent adverse events (TEAEs)**, defined as AEs with the first onset or worsening after the first IMP intake and not more than 14 days after the last IMP intake.

If the start date of an AE is incomplete or missing, it will be assumed to be treatment-emergent except if the incomplete start date or the stop date indicates that the event started or ended prior to the first IMP intake or started later than 14 days after last IMP intake.

AEs will be further assigned to the following categories:

- **Serious Adverse Events (SAEs):** defined as AEs considered by the investigator as serious.
- **Adverse Event of Special Interest (AESIs):** defined as AEs assessed by the investigator as being of special interest.
- **Related TEAEs:** defined as AEs assessed as being “Possible”, “Probable” or “Definite” to IMP and include the events with missing IMP relationship assessment.
- **Unrelated TEAEs:** defined as AEs assessed as being “Not related” or “Unlikely” to be related to IMP.
- **Severe TEAEs:** defined as AEs assessed as being “Severe” in intensity and include the events with missing severity assessment.
- **TEAEs leading to down-titration:** defined as AEs where “Action taken with study medication” is indicated as “dose reduced”.
- **TEAEs leading to discontinuation:** selected as those events where “Action taken with study medication” is indicated as “drug withdrawn” or “other actions” is “discontinued from study”.
- **TEAEs leading to death:** selected as those events where outcome of event is indicated as “fatal”.

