### **5.6.3 Arterial Blood Gas Analysis**

Arterial blood gas analysis will be performed at visit A1 and MPV3 before first IMP intake.

The following parameters of Arterial blood gas analysis will be collected:

- Fraction of inspired oxygen (%) (**FiO2**)
- pH
- oxygen partial pressure (mmHg) (**pO2**)
- carbon dioxide partial pressure (mmHg) (**pCO2**)
- bicarbonate (mEq/L)
- base excess (mEq/L) (**BE**)
- arterial oxygen saturation (%) (**SaO2**)\*
- sodium (mEq/L)
- potassium (mEq/L)
- lactate (mEq/L)

\* - Collected as “O2 content (%)” in earlier eCRF versions.

If arterial blood gas analysis is not performed, then peripheral oxygen saturation (%) will be collected.

The clinical significance (yes/no) of any abnormal Arterial blood gas analysis findings will be assessed by the investigator. Parameter values without a clinical significance evaluation will be considered as “Normal”, and values with “No” or “Yes” clinical significance evaluations will be considered as “NCS Abnormal” and “CS Abnormal”, respectively.

The following statistical output will be provided:

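### For ECG and blood gas, a blank clinical-significance field is read as 'Normal' even where the recorded finding or value is abnormal

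*SAP*

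**What the plan says.** The two sections work the same way. For ECG: "Clinical significance (yes/no) of any abnormal ECG data findings will be assessed by the investigator". For blood gas: "The clinical significance (yes/no) of any abnormal Arterial blood gas analysis findings will be assessed by the investigator". Each then states: "Parameter values without a clinical significance evaluation will be considered as" Normal. An entry of 'No' becomes abnormal but not clinically significant (NCS), and 'Yes' becomes abnormal and clinically significant (CS). Neither section gives a reference range, a comparison with the recorded finding, or a category for an abnormal result whose significance was not assessed.

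For repeated ECGs the SAP adds: "For abnormality assessments, the worst value within the visit/timepoint will be used". For the ECG incidence table: "Percentage will be based on the number of patients at specified visit". The blood-gas incidence table uses the same denominator.

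The outputs built on this classification are Tables 15.3.3.2 and 15.3.3.3 (blood gas) and 15.3.5.4.1 to 15.3.5.4.3 (ECG). Clinically relevant changes in ECG and in laboratory parameters, including blood gas, are named safety endpoints (Protocol 13.1.2.1, SAP 2.2.2.1).

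**The concern.** A blank CS field can arise in two ways. The investigator judged the result normal, so nothing was due; or the result was abnormal and the field was not completed. The rule gives both the same label and does not consult the recorded data that could separate them.

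The clearest case is heart rhythm. SAP 5.6.5 lists it with its own normal/abnormal entry, so a rhythm recorded as abnormal with a blank CS field would be tabulated as 'Normal', against the recorded data. A numeric ECG or blood-gas value outside its reference range would be treated in the same way.

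The SAP classifies from the value elsewhere. Haematology, coagulation and biochemistry are graded low, normal or high against the laboratory range (5.6.2), and catheterisation results are graded against tabulated ranges after investigator significance was set aside (5.5.1). At stake is the accuracy of the abnormality tables for named safety endpoints in the first study of this drug in PAH patients.

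**Working it through.** **Step 1: the possible cases.** Setting the rule against what may have been recorded:

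| Recorded finding | CS field | Class under the SAP | Agrees with the record? |
|---|---|---|---|
| Normal | blank | Normal | yes |
| Abnormal | No | NCS abnormal | yes |
| Abnormal | Yes | CS abnormal | yes |
| Abnormal | blank | Normal | no |

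Only the last row fails. Its frequency depends on how often an abnormal finding was left without a CS entry, which the documents do not report.

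**Step 2: direction of the error.** In the incidence tables the patient stays in the denominator and leaves the numerator, so incidence can only be understated. In the shift tables it depends on which entry is blank:
- Normal to abnormal, later entry blank: shown as normal to normal. A new abnormality is lost.
- Abnormal to abnormal, baseline entry blank: shown as normal to abnormal. An old abnormality looks new.
- Abnormal to abnormal, later entry blank: shown as abnormal to normal. An apparent improvement.
- Abnormal to normal, baseline entry blank: shown as normal to normal. An improvement is lost.

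**Step 3: illustrative size.** The plan has no figure of its own to reproduce. Inputs: N = 32 (Protocol 13.3). Assumed: a truly abnormal patients at a visit, and a probability m that the CS entry is omitted for an abnormal finding.

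Single recording: expected reported count = a(1 − m); chance that at least one abnormal patient appears as Normal = 1 − (1 − m)^a. For a = 8 (8/32 = 25.0%):

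| m | Reported count | Reported % | Chance of at least one error |
|---|---|---|---|
| 5% | 7.60 | 23.8 | 34% |
| 10% | 7.20 | 22.5 | 57% |
| 20% | 6.40 | 20.0 | 83% |

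Over a = 4 to 12 and m = 5% to 20%, the chance of at least one error runs from 19% (a = 4, m = 5%) to 93% (a = 12, m = 20%).

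Triplicate ECGs, if all three recordings are abnormal and omissions are independent: expected count = a(1 − m³). For a = 8 and m = 20%: 8 × (1 − 0.008) = 7.94, or 24.8%. The loss is then negligible. If the whole timepoint goes unassessed, or only one of the three recordings is abnormal, the single-recording figures apply.

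One misclassified patient is 1/32 = 3.1 points overall. The tables are also split by highest tolerated dose; in an assumed group of 8, one patient is 1/8 = 12.5 points.

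**Step 4: where it applies.** Triplicates are taken only at A1 and MPV3. ECGs at V1, A3/B3/C3/D3, MPV1, MPV2, EDV and follow-up are single, and patients enrolled under protocol version 1.0 had single ECGs throughout. The SAP has no repeat-measurement rule for blood gas.

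**Step 5: stated safeguards.** Protocol 15.4 provides completeness and consistency checks, and queries for missing key data, but does not say that a blank CS field counts as key data. Deviation PD#32 in SAP section 6 covers missing or incomplete ECG assessments, graded minor, and does not name blood gas. Neither is stated to catch the failing row.

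**The case against.** The strongest reply is that a blank is mainly a coded answer. Because CS is requested only for abnormal findings, the rule decodes a conditional field, and the SAP revision history shows it was specified in the draft that followed the Data Review meeting. Investigators also assess each printed ECG (Protocol 11.3.5) and must review laboratory reports for clinical relevance (Protocol 11.3.2). This stands: most blanks are probably correct, and an abnormal finding may never have been left blank.

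Several stronger readings are tempting, and the documents do not support them.
- *The rule contradicts the adverse-event rules*, under which severe events "include the events with missing severity assessment". Severity and causal relationship are due for every adverse event (Protocol 12.2), so a blank there is truly missing. A blank CS field is expected for every normal result.
- *It breaches SAP 4.1*, under which "the number of missing values will be displayed as" a separate category. That provision applies only where appropriate and present.
- *It could hide a QT signal*, given the hERG and dog QT findings in Protocol 6.2.1. QT and QTcF are still summarised numerically, with changes from baseline and from pre-dose, and are listed. Blood-gas values are likewise summarised and listed. None of these outputs uses the CS rule.
- *The bias always favours the drug.* A blank at baseline can make an old abnormality look new.

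What survives is narrow: nothing in the text stops a recorded abnormal finding from being tabulated as Normal.

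**Conclusion.** The point holds as a limited misclassification risk in five categorical safety tables. It arises only when an abnormal finding or out-of-range value has a blank CS field. Single ECGs and blood gas are exposed; triplicate ECGs are largely protected if at least one abnormal recording was assessed.

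The size cannot be estimated from the documents. The 3.1 points is simply one patient out of 32, and the figures of 20.0% to 23.8% for a true 25.0% rest on assumed abnormality and omission rates. The conclusion that the rule can override recorded data depends on none of these assumptions; it follows from the wording. The correction is worth making because it is cheap and the tables report named safety endpoints. It gives no ground for doubting the numeric ECG and blood-gas summaries.

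**What to change.** Amend SAP 5.6.3 and 5.6.5 so that a blank CS field means 'Normal' only where nothing recorded contradicts it. Otherwise:
- If the eCRF records the finding as abnormal or present, class it as 'Abnormal, CS not assessed'. This covers heart rhythm and the five morphological items (P pulmonale, right axis deviation, RV hypertrophy, RV strain, right bundle branch block), which have no numeric range.
- If a numeric value lies outside a reference range stated in advance, give it the same class. Use site or laboratory reference ranges. Table 5 for catheterisation is not a suitable model for limits: it lists mPAP of 25 mmHg or more as normal, which is the study's own diagnostic threshold for PAH.
- Query each such entry, show the category in the incidence and shift tables, and report the count and a listing.

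The cost is a few sentences in the SAP, a programmed check, one more row in the table shells, and citing reference ranges that the SAP does not now contain for these parameters. The drawback is that a few marginal values the investigator judged normal may fall into the 'not assessed' category; keeping that category separate from NCS and CS abnormal limits the harm.

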Zamicastat had no or only slight effects on the action potential parameters in the dog Purkinje fiber at 0.222 µg/ml (measured concentration) and higher pro-arrhythmic potential related to lengthened action potential duration at 90% repolarization (APD90) and enhanced action potential triangulation (APT) at the measured concentration of 1.930 µg/ml. In a study that evaluated the effects of zamicastat on hERG potassium channel the IC₅₀ was determined to be 113.84 ng/mL, and no difference from the vehicle group was observed up to 39.2 ng/mL of zamicastat. These concentrations (up to 39.2 ng/ml) exceed by 22 times the free maximum observed plasma concentration at steady state (C_{max}) of zamicastat in human plasma at zamicastat doses of 200 mg/day after repeated administration for 10 days under fed conditions and micronized API (BIA-51058-116). In a chronic toxicity study in non-rodents, zamicastat was administered by oral capsule to beagle dogs for 6 months at dose levels of 30, 60 or 90 mg/kg/day in Week 1 and 10, 30 or 60 mg/kg/day thereafter followed by a 7-week recovery period. Electrocardiogram measurements showed decreases in heart rate for treated groups only during Week 13 when compared with control and pretreatment. Increases in QT and QTc interval were observed during Weeks 13 and 26 for all treated groups. These alterations did not result in any clinically detectable evidence of cardiac malfunction in the dogs. There was less of an effect at end of recovery phase, indicating partial recovery, and as no heart lesions were seen during the histopathological examination, in the context of this study the changes were considered non-adverse. Zamicastat has undergone a comprehensive toxicological evaluation in studies of appropriate design consistent with ICH requirements in the mouse, rat and dog. Embryofetal development studies have been conducted in rats and rabbits and fertility studies and pre- and post-natal development toxicity have been conducted in rats. Administration of zamicastat was associated with dose-dependent increases in zamicastat plasma levels. Table 1 indicates the extent of exposure [area under the plasma concentration-time curve up to the last measurable concentration (AUC_{0-t})] of zamicastat and its metabolite BIA 5-453 corresponding to the no-observed adverse effect level (NOAEL) at the end of treatment with zamicastat in toxicity studies.

Table 1: Extent of exposure of zamicastat and its metabolites

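### As SAP 5.6.5 reads, no numeric ECG table gives the paired change from the drug-free baseline at 4 h or 8 h post-dose at MPV3

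*SAP*

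**What the plan says.** At A1 and MPV3 the SAP (5.6.5) plans triplicate ECGs "before IMP intake as well as 4 and 8 hours after IMP intake", which makes nine recordings per visit. Three sets of numeric tables use them.

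- **Tables 15.3.5.1.1-2:** "ECG parameters will be summarised including change from baseline at each visit by HTD and overall".
- **Tables 15.3.5.2.1-2:** to assess short-term effects, "the absolute change from the pre-dose value within the corresponding visit will be calculated for each parameter at visits A1 and MPV3". The table description reads "The observed values and absolute changes from the pre-dose value will be summarised for each vital sign parameter at each timepoint by HTD and overall". It names vital signs under an ECG title, evidently a carry-over from section 5.6.4.
- **Tables 15.3.5.3.1-2:** the MPV3 within-visit change minus the A1 within-visit change, timepoint by timepoint.

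The averaging rule is: "Where multiple ECG recordings are performed within a visit or timepoint, ECG parameters will be summarised as follows". It continues: "For numeric parameters, the mean of collected values will be used in summaries". SAP 4.7 sets baseline as the last non-missing value before first intake, so baseline is drug-free.

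Vital signs are measured at A1 and MPV3 on a similar schedule, but SAP 5.6.4 says: "Vital sign parameters will be summarised including change from baseline at each timepoint by HTD and overall".

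**The concern.** Change in ECG is a listed safety endpoint. The recordings at MPV3 4 h and 8 h appear to be the only scheduled post-dose ECGs above 50 mg. A1 follows a single 50 mg dose. At A3 to D3, MPV1 and MPV2 the patient comes in undosed, trough blood is drawn before intake, and the ECG precedes the blood draw (Protocol 10.3.1, 11.3.5 and 11.6.4 to 11.6.6), so those ECGs are at trough.

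The natural summary of the MPV3 recordings is QTcF at 4 h and 8 h minus the drug-free value, patient by patient. The by-visit table appears to dilute it, and the two short-term tables subtract whatever drug effect is already present at trough. If QTcF rises with concentration, every planned numeric change would lean towards showing too little. The protocol gives a reason to look. It reports a hERG IC50 and, in the 6-month dog study, "Increases in QT and QTc interval were observed during Weeks 13 and 26 for all treated groups".

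**Working it through.** **Which output contains the target quantity?** The target is the paired change, MPV3 at 4 h or 8 h minus drug-free baseline.

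| Output | Reference | MPV3 4 h and 8 h shown separately? | Paired numeric change from drug-free baseline? |
|---|---|---|---|
| 15.3.5.1.x | drug-free | no, by visit (literal reading) | only for the visit mean |
| 15.3.5.2.x | MPV3 pre-dose, on drug | yes, with observed values | no |
| 15.3.5.3.x | MPV3 pre-dose, less the A1 change | yes | no |
| 15.3.5.4.2 | drug-free | worst assessment in the visit | no, categories only |
| Listing 16.2.4.5 | none | individual values | no |

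The MPV3 pre-dose value is on drug because Protocol 6.2.2 puts steady state at Day 3 to Day 5.

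**How much could be lost?** The documents give no QTcF effect or SD, so there is no plan figure to reproduce. The calculation below is illustrative. Its only document input is the range of mean AUC accumulation ratios in Protocol 6.2.2, R = 1.095 to 3.462. It assumes an effect proportional to concentration, a stationary one-compartment model and 24 h dosing.

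From R = 1/(1 − e^(−24k)), k = −ln(1 − 1/R)/24. With decline only and a unit dose, the steady-state effect at time t is R·e^(−kt), and the pre-dose effect is R − 1.

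- R = 1.095 (half-life 6.8 h): pre-dose 0.095, 4 h 0.729, 8 h 0.485. Within-visit share at 4 h = (0.729 − 0.095)/0.729 = 87%. Visit mean = (0.095 + 0.729 + 0.485)/3 = 0.436, which is 60% of the 4 h effect.
- R = 3.462 (half-life 48.8 h): pre-dose 2.462, 4 h 3.271, 8 h 3.090. Within-visit share = 0.809/3.271 = 25%. Visit mean = 2.941, which is 90%.

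Adding first-order absorption (ka 0.3 to 1.5 per h, assumed), the steady-state effect is ka/(ka − k)·[e^(−kt)/(1 − e^(−24k)) − e^(−ka·t)/(1 − e^(−24ka))]. Shares are of the larger of the 4 h and 8 h effects:

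| R | Visit mean (15.3.5.1) | MPV3 within-visit (15.3.5.2) | MPV3 minus A1, HTD 200 mg (15.3.5.3) | Same, HTD 50 mg |
|---|---|---|---|---|
| 1.095 | 60-71% | 78-87% | 57-64% | −7 to −4% |
| 1.5 | 75-84% | 47-60% | 32-43% | −16 to −7% |
| 2.0 | 82-89% | 33-44% | 21-31% | −14 to −6% |
| 3.462 | 90-94% | 18-25% | 11-17% | −9 to −4% |

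**Is the extreme plausible?** The fraction of steady state reached after n doses is 1 − (1 − 1/R)^n. At R = 3.462 this is 74% after four doses and 82% after five, which sits badly with Day 3 to 5. At R = 2.0 it is 94% and 97%, which is compatible. At R = 2.0 the within-visit change still shows less than half the effect.

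**The case against.** Five points on the other side deserve weight.

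1. A reader might infer that no ECG table sets post-dose steady-state recordings against the drug-free state. That is not so. Table 15.3.5.4.2 shifts baseline against the worst MPV3/EDV assessment, and the endpoint is worded as clinically relevant change. This stands. However, the table is categorical, and a value without an investigator rating counts as normal, so a QTcF rise that nobody flags does not appear.
2. Tables 15.3.5.2.x print observed values by timepoint, so a difference of group means can be formed by hand. True, but it carries no SD of the change and may mix different patients, since version 1.0 patients had no A1 ECG.
3. Pooling is the literal reading, not the only one. The averaging rule speaks of a visit or a timepoint, and the table shells are a separate file not among the documents at hand; they may already have timepoint rows. This stands. Nor is baseline itself contaminated, because SAP 4.7 fixes it before first intake. Version 1.0 patients had one ECG per visit, so nothing is pooled for them.
4. A reader might infer that a QTcF effect would be mostly subtracted out. The arithmetic does not support that in general: at R = 1.095 the within-visit change keeps 78-87%. The two sets of tables also compensate. In the decline-only model the better of visit mean and within-visit change never falls below about 70% (near R = 1.31). The protocol also describes the pharmacokinetics as time-dependent, which weakens any half-life derived from R.
5. The short-term tables are labelled as such and do not claim to show the total effect. The wider evidence is also fairly reassuring. The hERG no-effect concentration was 22 times free Cmax at 200 mg/day, the dog changes were judged non-adverse, and a dedicated human study found no clinically significant repolarisation effect at a single 400 mg dose and a minimal one at 1200 mg. This lowers the urgency. That study used single doses in healthy adults, and Protocol 8.2 expects that PAH may alter the pharmacokinetics.

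**Conclusion.** The point holds in a limited form. As the text of SAP 5.6.5 reads, no numeric ECG table gives the paired change from the drug-free baseline at MPV3 4 h or 8 h. The by-visit table averages that change with the pre-dose recordings, and at A1 it mixes drug-free with post-dose recordings. Tables 15.3.5.2.x and 15.3.5.3.x measure fluctuation within a dosing interval, not the total effect.

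The size depends on accumulation. Over the protocol's range the visit mean shows about 60-94% of the effect and the MPV3 within-visit change about 18-87%. The MPV3-minus-A1 difference shows about 11-64% at an HTD of 200 mg and slightly less than zero at 50 mg. These shares rest on the proportional-effect, one-compartment and absorption assumptions above, and the lowest within-visit figures need a half-life that the stated time to steady state hardly allows. They do not show that a QTcF effect exists or that the plan would hide one altogether. This is a reporting gap worth closing, all the more so because the SAP already uses the right summary for vital signs.

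**What to change.** State in SAP 5.6.5 that Tables 15.3.5.1.1-2 report A1 and MPV3 by timepoint (pre-dose, 4 h, 8 h), with triplicates averaged only within a timepoint. Give change from the mean of the A1 pre-dose triplicate, or from V1 for patients under protocol version 1.0. SAP 4.7 does not by itself say whether a triplicate baseline is the mean or the last recording, so this needs saying. The SAP does not give the time relative to dose of the single MPV3 recording in version 1.0 patients, so show it on its own row.

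Keep Tables 15.3.5.2.x and 15.3.5.3.x, with a footnote that the MPV3 pre-dose value is on drug, and correct the reference to vital signs in the description of 15.3.5.2.x. If the shells already show timepoints, only the SAP sentence and the footnote are needed.

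The cost is a sentence or two of SAP text and extra rows in two tables. No new data are required.
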